Cost Measurement. Costs to be collected can be grouped into three broad categories: intervention delivery costs, participant time costs, and health care costs. Intervention costs incurred to develop both interventions will be excluded from the analysis as these costs have already been incurred and are thus “sunk” costs. Intervention Delivery Costs for both conditions will be estimated using both standardized estimates and convenience sampling of support staff and our interventionists. The time it takes to prepare for and execute CBT for SUD is specified in the treatment manual but will be assessed through a data tracking system, surveys, and counselor records to validate these estimates. Similar methods will be used to estimate time spent in identifying veterans with AUD, contacting veterans, and training veterans on the use of the mCM smart phone app. To reduce burden, we will not measure every activity for every subject for every occasion. Instead we will collect a convenience sample of observations toward the beginning and the end of the study to account for the fact that there may be a learning curve effect. The size of the convenience sample will depend on the variability we observe in the activity times—the larger the variability the larger the sample we will collect. In addition to labor costs, materials costs, including the cost of the mCM will be included.

Participant Time Costs (i.e., the opportunity costs to participants). This will include the time spent by participants in using the intervention strategies, techniques, or information. As part of the end-of-treatment follow-up, time spent on the intervention materials other than that involved in the treatment sessions will be assessed. In the intervention arm, the number of videos submitted will be used to assess the time involved in providing bioverification as part of mCM. We will derive participant time cost estimates for each group by combining the time estimates with standard wage estimates adjusted for age, gender, and if possible race, derived from the Statistical Abstract of the United States. Because we chose to conduct the cost-effectiveness analysis from the societal perspective, the use of mean wage rates has higher generalizability and validity than self-reported wages by the subjects. *Health care costs* will be obtained from VA medical records for outpatient, inpatient and medication use one year prior to trial enrollment and through the final follow-up.

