Cost and Effectiveness Measurement. Our primary cost effectiveness outcome measure will be the incremental cost-effectiveness ratio (ICER), with costs as the numerator and effectiveness as measured by QALYs as the denominator. Costs will include: intervention delivery costs, participant time costs and health care costs as described above. The QALY is a standardized effectiveness measure, based on the EuroQol (EQ-5D5L), that allows for the comparison of the value of a particular intervention to a broad range of other potential health care investments. Differences in reduction in heavy drinking days and secondary drinking outcomes (e.g., abstinence) among veterans in the mCM+CBT and the CBT comparison group will allow us to identify changes in the QALY effectiveness measure across groups. To estimate the QALYs, we will employ the methods and estimates developed by Barbosa and colleagues (2010), who used a Markov model to assign utility weights to a range of drinking patterns for medical morbidity and mortality, adjusted for health-related quality of life. Incremental costs and effectiveness of mCM+CBT will be compared to those of the CBT comparison group.

D.7. Optional Study Procedure

One of our study therapists, [name], is seeking licensure as a Licensed Professional Counselor, and as part of her supervision, needs to provide video recordings of therapy sessions to her supervisor, [name], MS, LPCS for review. Data will be shared with [name] as view only in a Duke Box folder to which only [name], [name], and [name] have access. Data will be shared in accordance with a data agreement facilitated by Duke’s Office of Research Contracts, and signed by [name] and [name]. This study procedure is fully optional, and is indicated as such during the informed consent process.

D.8. Measures

Participants will complete measures at primary assessment time points (baseline, post-treatment, 6 months post-quit date, and 12 months post-quit date), as well as reporting on alcohol at each CBT session. Follow-ups will be completed in-person.

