The PI will meet at least weekly with study personnel to discuss participants' reactions to the intervention, proper delivery of the intervention, and any adverse events or unanticipated problems. Monthly meetings between the investigators and the project manager will allow for ongoing progress reports, including the number of participants currently involved in the study groups, attrition rates, and scheduled data collection from participants, as well as notification and review of any AEs. Safety monitoring for adverse events will be conducted in real time by the PI and/or project manager. The following information about adverse events will be collected: 1) the onset and resolution of the AE, 2) an assessment of the severity or intensity, 3) an assessment of the relationship of the event to the study (definitely, probably, possibly or not related), and 4) action taken (e.g., none, referral to physician, start or increase concomitant medication). The PI will determine the severity of the event, will assign attribution to the event, and will monitor the event until its resolution.

F. STATISTICAL ANALYSES AND POWER CONSIDERATIONS

Variables of interest will be examined using means, standard deviations, and distributions (for continuous variables) and their frequencies (for categorical variables). For normally distributed outcome variables, linear statistical models will be used by default. However, examination of residuals and Q-Q plots will be undertaken to determine whether generalized linear modeling may be more appropriate. We will first conduct preliminary analyses to ensure that there are no differences across treatment groups with respect to gender, age, educational history, socioeconomic status, baseline alcohol consumption, PTSD symptoms, and depressive symptoms. In addition, we will evaluate potential effects of psychiatric variables on the treatment response. We do not expect differences to arise on these measures as a result of randomization. Nevertheless, we will potentially use covariate adjustment to address unanticipated differences in baseline variables. We will conduct sensitivity analyses to determine how variability in demographic/baseline variables influence estimates of treatment effects (Thabane et al., 2013).

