Aim 2: To examine the hypothesis that mCM paired with CBT for SUD will be more cost effective over the lifetime than CBT alone, cost-effectiveness analysis (CEA) will be performed using the incremental cost-effectiveness ratio (ICER), with costs as the numerator and effectiveness as measured by quality-adjusted life years (QALY) as the denominator. QALYs incorporate changes in quality of life (morbidity) using a set of values, one for each possible health state, reflecting the relative desirability of the health state (Drummond et al., 2009). Quality of life ratings, or utilities, will be derived from a prior study of the utility of different drinking states that used the standard gamble technique in a community/clinic sample of 200 individuals (Kraemer et al., 2005). The mean utility values (and standard deviations) calculated for each state were as follows: abstinent 0.93 (0.15), moderate drinking 0.88 (0.22), at-risk drinking 0.82 (0.27), meeting criteria for mild AUD 0.75 (0.29), meeting criteria for severe AUD 0.67 (0.29), and in recovery from alcohol dependence 0.83 (0.24). QALY change will be calculated based on change from baseline to 12-month drinking status. Prior to CEA, CBT alone will be assessed for dominance to determine whether it is both less costly and more effective than combined mCM and CBT. In the absence of dominance, an incremental cost-effectiveness ratio (ICER) will be computed to estimate the additional cost required to achieve one additional QALY. Specifically, the ICER combines the costs of the treatments with the QALY changes, using the cost in the mCM group over and above the control, divided by the incremental QALYs in the mCM group over and above the control. Given likely skewed economic data, nonparametric bootstrap resampling will be used to test the sensitivity of the calculated ICERs and cost-acceptability curves estimated to assess the probability that the mCM intervention is cost-effective at thresholds up to \$50,000 or \$100,000 per QALY (Willan & Briggs, 2006). Numerous sensitivity analyses will be conducted to evaluate the robustness of these results given varying estimates of abstinence rates, relapse to any heavy drinking, mortality rates, and long-term costs of sustained alcohol use. Cost-effectiveness analysis will be conducted if the primary outcome is significant; otherwise, a cost minimization analysis will be conducted.

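### One year of pre-enrolment VA cost is collected, but no use of it is pre-specified, so incremental cost is estimated less precisely than the planned data allow

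*Combined protocol and SAP*

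**What the plan says.** All references are to the combined protocol and SAP.

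- **Collection.** Section D.6 (Cost Measurement) takes outpatient, inpatient and medication cost from VA records for "one year prior to trial enrollment and through the final follow-up". Table 3 also schedules health-care utilisation at screening.
- **Numerator.** Section D.6 (Cost and Effectiveness Measurement) states: "Costs will include: intervention delivery costs, participant time costs and health care costs as described above". The description it points back to includes the pre-enrolment year, and nothing says that this year is left out of the ICER.
- **Incremental cost.** Section F (Aim 2) gives the only definition: "using the cost in the mCM group over and above the control".
- **Uncertainty.** The same paragraph states: "Given likely skewed economic data, nonparametric bootstrap resampling will be used". Cost-acceptability curves are also planned.
- **General adjustment.** The opening of section F says that "we will potentially use covariate adjustment to address unanticipated differences in baseline variables". The variables it will compare across arms are demographic items, baseline drinking, PTSD symptoms and depressive symptoms. Prior cost and utilisation are not among them.
- **Other outcomes.** The heavy-drinking models in section F (Aims 1 and 3) name the baseline value as a covariate, and Aim 2 bases QALYs on change from baseline. Cost is the outcome for which a baseline is collected and given no role.
- **Randomisation.** Section D.3 stratifies only on comorbid non-tobacco SUD, so prior cost is not balanced by design.

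**The concern.** Prior cost is often the best available predictor of later cost, and here it will be in hand at no extra effort. If it is left out of the estimator, chance differences between arms in prior cost carry through to follow-up cost and widen the interval around incremental cost.

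The cost difference matters in two places in section F (Aim 2). It enters the dominance check made before any ICER is computed. It is also all that remains if the primary outcome is not significant, because the plan then switches to cost minimisation.

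There is an issue of discretion as well. An adjustment that may or may not be used, depending on what the baseline table shows, leaves the analyst to choose the estimator after seeing the data.

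**Working it through.** **The plan's own cost figure.** The plan gives no SD, precision or sample size for cost. The one cost it does quantify is the ticket payout. From Table 2, the expected value per ticket is (239×1 + 125×2 + 65×5 + 40×10 + 30×20 + 1×100)/1000 = $1.914. The maximum number of tickets is 34 + 7×40 = 314, and 314 × 1.914 = $601, which matches the plan. This is the payout at perfect adherence. Staff time, app training, materials and participant time come on top, so it is not the full cost of CM.

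**Inputs**
- 140 randomised (section D.2), taken as 70 per CM arm. Equal allocation is an assumption.
- Cost SD: not in the documents. $5,000 and $20,000 are assumed to show a range.
- Correlation r between prior-year and follow-up cost: not in the documents. 0.3, 0.5 and 0.6 are assumed.
- The same SD in both periods is assumed.

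**Step 1: standard error of an unadjusted difference in mean cost.** SE = SD × √(2/70) = 0.169 × SD. This is $845 at SD $5,000 and $3,381 at SD $20,000.

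**Step 2: how much of a prior-cost imbalance carries over.** An imbalance does not pass one for one into follow-up cost. The expected shift from a one-SE imbalance is r × 0.169 × SD.

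**Step 3: gain from linear adjustment.** Adjusted SE = SE × √(1 − r²). The factors are √0.91 = 0.954, √0.75 = 0.866 and √0.64 = 0.800. The equivalent gain in sample size is 1/(1 − r²) = 1.10, 1.33 and 1.56.

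| r | Shift, SD $5,000 | Shift, SD $20,000 | Adjusted SE, SD $5,000 | Adjusted SE, SD $20,000 | SE reduction |
|---|---|---|---|---|---|
| 0.3 | $254 | $1,014 | $806 | $3,225 | 5% |
| 0.5 | $423 | $1,690 | $732 | $2,928 | 13% |
| 0.6 | $507 | $2,028 | $676 | $2,704 | 20% |

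**Step 4: check under skewness.** The factor √(1 − r²) is only approximate for skewed costs. In a log-normal simulation (assumed mean $10,000, SD $20,000, 70 per arm), linear adjustment reduced the SD of the estimated difference from $3,368 to $3,103 at an observed correlation of 0.32 (3,103/3,368 = 0.92). At an observed correlation of 0.68 it fell from $3,482 to $2,278 (2,278/3,482 = 0.65). The direction and rough size agree with the formula.

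**The case against.** **The plan does not commit to a raw difference.** Section F (Aim 2) says what an ICER is and does not state an estimator, and the opening of section F leaves room for adjustment. A reader might infer that the plan fixes an unadjusted comparison, but the text does not go that far. What stands is narrower: no adjustment for prior cost is pre-specified, and the list of variables to be compared omits it.

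**Nothing here is biased.** Under randomisation the unadjusted difference has the right expectation, and the planned bootstrap and acceptability curves already carry chance imbalance into the reported uncertainty. This stands in full. The point concerns precision and pre-specification.

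**Chance imbalance has not been shown to swamp the cost of CM.** A reader might set the $845 or $3,381 from Step 1 beside the $601 payout and conclude this. The comparison fails twice. It leaves out r: at SD $5,000 a one-SE imbalance shifts incremental cost by $254 to $507, below $601 throughout. And $601 is one component of CM cost, at maximum adherence. At SD $20,000 the shift does exceed $601, but the documents supply neither the SD nor r.

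**Adjustment leaves most of the noise.** This also stands. At SD $20,000 and r = 0.5 the SE falls only from $3,381 to $2,928, so a few costly patients during follow-up could still decide the sign.

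**The incentive arm and SUD stratum are already handled by the factorial design and the stratified blocks.** No precision gain can be claimed for adding them. They may enter the model as design factors.

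**Conclusion.** The gap is real and modest. The plan collects a baseline for cost, gives it no stated role, and does not exclude the pre-enrolment year from the numerator. The cost is lost precision: about 5%, 13% or 20% of the SE of incremental cost at an assumed r of 0.3, 0.5 or 0.6, worth about 10%, 33% or 56% more patients for this comparison. These percentages do not depend on the cost SD. They do rest on the assumed r and on linear adjustment, and they are approximate for skewed costs. The dollar shifts also rest on an assumed SD, equal in both periods, and on 70 per arm.

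The documents do not support a claim of bias, or a claim that imbalance in prior cost will dominate the result.

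**What to change.** Add to section F (Aim 2):

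1. State that the ICER numerator covers post-randomisation costs only, and that the pre-enrolment year is used as a covariate.
2. Estimate incremental cost by regression on CM arm with prior-year VA cost as a covariate. The incentive arm and SUD stratum may be included as design factors.
3. Name the model form for skewed costs in advance, for example a GLM with stated family and link, or a cost equation fitted jointly with the QALY equation. Refit it in each bootstrap sample.
4. Use the same estimator if the analysis switches to cost minimisation.
5. Report the unadjusted difference as a sensitivity analysis.

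The cost is a few sentences in the SAP and a small amount of code. The data are already planned, and no visit, measure or patient is added.

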Our long-term goal is to implement cost-effective treatments that reduce the morbidity and mortality associated with alcohol and substance misuse. VA has widely implemented evidence-based cognitive-behavioral therapy (CBT) for treatment of substance abuse disorders (Karlin & Cross, 2014). The primary goal of the current study is to evaluate the clinical effectiveness and cost effectiveness of CM as an adjunct to CBT for AUD. The trial will also explore the potential utility of a long-term abstinence incentive on treatment utilization and alcohol outcomes. We plan to conduct a comparative effectiveness trial with a 2 x 2 factorial design in which 140 veterans with AUD will be proactively recruited and randomized to receive either CM as an adjunct to state-of-the-art evidence-based CBT, or receive CBT alone; and to one of two long-term incentive conditions (i.e., receipt of a monetary incentive for abstinence/low-risk drinking at 6-months vs. no incentive). Specific aims include:

AIM 1: To evaluate the effectiveness of mobile contingency management, as an augment to evidence-based CBT for AUD, on (1) treatment engagement and retention, and (2) reduction in heavy drinking days and abstinence from alcohol at post-treatment, 6-month and 12-month follow-ups.

Hypothesis 1a: Mobile contingency management for AUD will be associated with greater treatment engagement and treatment completion.

Hypothesis 1b: Mobile contingency management for AUD will be associated with decreased self-reported heavy drinking days and increased rates of abstinence from alcohol at each follow-up.

AIM 2: To evaluate the cost effectiveness of CM as an adjunct to evidence-based CBT for SUD in quality adjusted life years (QALY).

Hypothesis 2: CM paired with CBT will result in greater cost-effectiveness compared to the CBT alone as measured by the incremental cost-effectiveness ratio.

AIM 3: To explore the effects of a long-term (six-month) abstinence incentive on (1) treatment utilization and (2) alcohol outcomes at the 6-month and 12-month follow-ups.

Hypothesis 3: A long-term abstinence incentive will (1) increase utilization of AUD aftercare and (2) be associated with reduced heavy drinking days and increased abstinence rates.

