As shown in Figure 3, proposed is a 2X2 factorial randomized clinical effectiveness trial testing the effects of combining CM as an adjunct to state-of-the-art, evidence-based CBT (CBT + CM vs. CBT only) and the effects of a single, long-term incentive for bioverified abstinence/no heavy drinking at 6-months follow-up (Long Term Incentive vs. No Incentive). All patients will be referred to standard aftercare and encouraged to participate in 12-step programs following the intervention. Use of aftercare and other health care utilization will be collected based on objective measures (VA electronic medical record) and participant report. Health-related quality of life will be collected at each follow-up. The primary endpoint (AIM 1) will be number of heavy drinking days in the past 30 days at the 6-month follow-up. Cost effectiveness analysis (AIM 2) will be performed using quality-adjusted life years (QALY) as the outcome. The utility of a long-term incentive (AIM 3) will be tested by examining use of aftercare and other alcohol-related treatment and heavy drinking days in the past 30 days at the 6 and 12-month follow-ups.

D.2. Patient Identification, Eligibility, and Recruitment

Patients will be identified from the Durham VA Health Care System (DVAHCS) using the hospital's computerized medical record. Records will be screened for AUD. After mailing introductory materials with an opt-out number, we will contact those who do not opt out via telephone to explain the study and recruit them for participation. If necessary, in order to reach female veterans, we can oversample women for the screening mailouts.

Figure 3. Trial Design

We will also utilize reactive recruitment methods as needed to reach potentially eligible veterans. For example, we will seek referrals from the DVAHCS Substance Use Disorders Clinic. In order to reach female veterans, we will seek referrals from the Women's Health Clinic. In addition, we will post IRB-approved flyers and brochures throughout the DVAHCS catchment area, especially in clinic areas and Vet Centers. In addition, we will post, if necessary, flyers and brochures in the community, in local restaurants, laundromats, university student centers, etc. We will also use online classified advertisements such as Craigslist.com to reach potential participants.

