D.8.7. Treatment Fidelity. Counselors will receive weekly supervision for CBT from [name] or another senior clinician. Following procedures recommended by the VA training program, we will utilize the Cognitive Behavioral Therapy for Substance Use Disorders Rating Scale to measure counselor adherence in delivering behavioral treatments for substance abuse disorders (Gnys, DeMarce, Raffa, & Karlin, 2014). A random selection of 10% of the counseling sessions will be rated for fidelity by rater who is otherwise independent of the conduct of the study. Fidelity ratings will be used in supervision to improve counseling. To measure therapeutic alliance, we will use the 16-item Individual Treatment Alliance Scale Revised Short Form, which has a demonstrated relationship with treatment dropout and treatment response in behavioral interventions (Pinsoff, Zinbarg, & Knobloch-Fedders, 2008). This measure will be given at the final treatment session for all participants, including participants who withdraw early from treatment.

D.8.8. Outcome Measurement and Biochemical Verification. At each treatment session, and at post-treatment and follow-ups, we will measure number of heavy drinking days (> 5 drinks in day for men, > 4 drinks in a day for women), binge drinking episodes (heavy drinking within a 2-hour period), number of drinking days, and drinks per drinking day. At follow-ups, we will conduct Timeline Follow-back interviews to improve self-reports of drinking behavior over the previous months. We will ask participants to complete items from the Addiction Severity Index (ASI) to assess the consequences of substance use on functioning in the previous month. Participants will complete all of the items of the Employment subscale, and items 1, 3, 7, 8, 9, 10, 28, 29, 30, 31, 32, and 34 of the Family/Social subscale. Early continuous abstinence will be defined as three consecutive weeks of alcohol abstinence in the first eight weeks after the quit attempt, a threshold that has been predictive of good long-term SUD outcomes (Carroll et al., 2014). We will bioverify self-reports of low risk drinking with fingerstick blood spot samples for PEth testing at 6-month and 12-month follow-ups.

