D.8.9. Quality of Life and Health Care Utilization. VA administrative data will be accessed via the VA Corporate Data Warehouse to provide objective measures of VA health care utilization. Our team has extensive experience accessing and utilizing VA data (Elhai, [name], & Ford, 2008; [name], Bosworth, Grambow, Dudley, & [name], 2002; [name], Bosworth, Stechuchak, Strauss, & Butterfield, 2006). Additionally, we will collect self-reported use of non-VA healthcare and 12-step programs and information about insurance coverage. Health care related quality of life will be assessed with the EuroQol (United Kingdom Alcohol Treatment Trial Team, 2005) at baseline and each of the follow-ups.

D.9. Participant Reimbursement

Participants will be paid as follows:

Project Milestone	Amount
Screening visit	\$50
CM abstinence reinforcement	\$611
End-of-treatment visit	\$50
6-month follow-up	\$100
Bioverified abstinence at 6 month follow-up (if randomized to long-term incentive condition)	\$300
12-month follow-up	\$125
TOTAL	\$1236

D.10. Potential Challenges and Solutions

One potential challenge to the success of this project is recruitment and retention. Previous AUD trials in veterans indicate lost-to-follow-up rates near 30% at 12 month follow-up (Hagedorn et al., 2013). We have implemented several methods to increase retention in our trials (e.g., pre-alert letters, birthday cards, reminder

calls, thank you notes) and have obtained excellent retention rates ($>80\%$ at 12-months) in substance using populations (e.g., homeless veterans). We will use these methods and have budgeted to provide an incentive to participants to complete each follow-up. Missing data will be treated as indicative of relapse/heavy drinking. Our pilot data and experience in previous trials indicate that proactive recruitment of veterans with AUD is feasible. To augment our proactive recruitment method, we could include reactive recruitment strategies and include referrals from the SUD clinic at DVHCS. Another potential concern is lost/stolen study equipment. We now have extensive experience with providing veterans with a smartphone and monitoring devices to perform mobile monitoring for CM (e.g., R34AA023877; R01CA196304; 1I01HX001109; 1I01RX001301) and have budgeted for anticipated lost/stolen equipment. Costs of lost equipment will be captured and included in cost analyses.

E. DATA AND SAFETY MONITORING

E.1. Risk/Benefit Ratio

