Power calculations provided below were performed with Power Analysis and Sample Size software (PASS, Version 12: NCSS LLC, Kaysville, Utah). The sample size estimate is based on the first hypothesis that the CM intervention will result in higher overall self-reported abstinence rates and fewer days of heavy drinking at 6-months post-randomization. As described in the analysis section, this hypothesis will be tested via linear contrasts specified within the context of MLM analyses. Because this will be tested using repeated-measures data, statistical power will depend on the effective sample size (ESS). The ESS is the number of statistically independent observations available for this study, which is equivalent to the total number of observations (number of participants x number of data collections) adjusted for within-individual correlations. As the intraindividual, or intra-class, correlation (ICC) decreases, the ESS increases. Given that we found an ICC of .20 for 7-day point prevalence measured at posttreatment, 3 months, and 6 months in an RCT with 218 smokers featuring CM as the experimental treatment (R01 CA196304), we anticipate a similar, if not smaller, figure in this trial, given longer intervals between observations. Using this ICC value, with 140 participants with up to 3 observations each, the ESS would be 300. Even with an unexpectedly high 15% attrition at each observation point, such that only 119 complete treatment, 101 6-month follow-up, and 86 12-month follow-up, the ESS for examining linear contrasts would be 227, which would be sufficient to detect treatment effects as small as Cohen's $d = 0.43$ with 90% power. Because the previous trial examining the effect of CM as an adjunct to behavioral treatment found large effects (Cohen's $d = 0.92$; McDonell et al., 2017) on heavy drinking days, our proposed sample size has sufficient statistical power.

G. PROJECT MANAGEMENT PLAN and TIMELINE

The scheduled project timeline is illustrated in Table 5. Members of this multi-disciplinary research team have experience in one or more key components of the

Activity	Year 1				Year 2				Year 3				Year 4				Year 5			
	1	2	3	4	1	2	3	4	1	2	3	4	1	2	3	4	1	2	3	4
Hire/Train Staff	■																			
Recruitment		■	■	■	■	■	■	■	■	■	■	■								
Intervention			■	■	■	■	■	■	■	■	■	■								
Follow-ups: post-txt, 6-and 12-months			■	■	■	■	■	■	■	■	■	■		■	■	■	■			
Data Analysis														■	■	■	■	■	■	■

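### In-person is the only follow-up mode given, so a missed 6-month visit leaves no primary endpoint value although a telephone interview could supply one

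*Combined protocol and SAP*

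**What the plan says.** The mode of follow-up is set in one sentence of D.8: "Follow-ups will be completed in-person". The plan gives no telephone, video or postal alternative, and no rule for a 6-month value that is missed.

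D.1 defines the endpoint: "The primary endpoint (AIM 1) will be number of heavy drinking days in the past 30 days at the 6-month follow-up". Hypothesis 1b makes clear that it is self-report, predicting "decreased self-reported heavy drinking days and increased rates of abstinence from alcohol at each follow-up". Table 3 lists study staff as completing the Timeline Follow-back and the heavy-drinking-day count, and D.8.8 describes the method: "At follow-ups, we will conduct Timeline Follow-back interviews to improve self-reports of drinking behavior over the previous months". The component that needs a sample is the verification of low-risk drinking by "fingerstick blood spot samples for PEth testing at 6-month and 12-month follow-ups".

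D.10 lists retention measures such as "pre-alert letters, birthday cards", reminder calls, thank-you notes and visit payments. These encourage attendance; none changes how the data are collected. The trial already uses the telephone for other purposes: in D.2, for those approached by mail, "we will contact those who do not opt out via telephone to explain the study", and D.3 adds a telephone screen.

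The power paragraph of Section F works through a 15% loss at each observation point, "such that only 119 complete treatment, 101 6-month follow-up, and 86 12-month follow-up".

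**The concern.** The primary outcome is a short structured interview about the last 30 days. Tying it to a clinic visit makes its availability depend on willingness and ability to travel, which the outcome itself does not require. Someone who has moved, has been admitted elsewhere or is drinking heavily may decline a visit but still answer a call.

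People who stay away are plausibly drinking more than those who come, so the gap is unlikely to be harmless. The payments in D.9 may add to this. In the long-term incentive condition the 6-month visit is worth $100 + $300 = $400 to a verified non-heavy drinker, against $100 to a heavy drinker.

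The analysis then has to bridge the gap by assumption. D.10 counts missing data as relapse or heavy drinking, which would favour whichever arm attends better. Section F uses maximum likelihood, which it ties to data missing at random, and multiple imputation from baseline measures. Neither is secure if drinking at month 6 drives absence at month 6. That these two rules disagree is a separate matter; here it is enough that both rest on assumptions that an observed value would make unnecessary.

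**Working it through.** **Inputs.** From Section F: 140 randomized; up to 3 follow-up observations each; ICC 0.20; 119, 101 and 86 observed under 15% loss per point; effective sample size (ESS) 300 without loss and 227 with it; d = 0.43 at 90% power. From D.10: loss near 30% at 12 months in earlier AUD trials in veterans, and retention above 80% at 12 months in the team's own trials. Assumed: two-sided alpha 0.05, which is not stated but fits the plan's figure, and the share of missed interviews that could be recovered, on which the documents give nothing.

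**1. The plan's figures reproduce.** A participant with m observations contributes m / (1 + (m − 1) × 0.20).
- No loss: 140 × 3 / 1.4 = 300.
- With loss, taking drop-out as permanent: 86 have three observations, 101 − 86 = 15 have two, 119 − 101 = 18 have one, and 21 have none. ESS = 86 × 3/1.4 + 15 × 2/1.2 + 18 × 1 = 184.3 + 25.0 + 18.0 = 227.3.
- Detectable d at 90% power = (1.960 + 1.282) × √(4/227) = 0.430.

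**2. Missing primary values at 6 months.**
- Stress case: 140 − 101 = 39, and 39/140 = 27.9%.
- 30% loss at 12 months, constant over three visits: 1 − 0.70^(2/3) = 21.2%, about 30 participants.
- 20% loss at 12 months, same assumption: 1 − 0.80^(2/3) = 13.8%, about 19 participants.

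**3. Effect of recovering a share f of the 39 in the stress case.** The number with the endpoint is 101 + 39f. For the ESS, a recovered participant moves from one observation to two, or from none to one. At f = 0.5: 184.3 + 25.0 + (9 × 1 + 9 × 2/1.2) + 10.5 = 243.8.

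| Share recovered (assumed) | With 6-month value | Missing | ESS | Power at d = 0.43 |
|---|---|---|---|---|
| 0 | 101 | 27.9% | 227 | 90.0% |
| 25% | about 111 | 20.9% | 236 | 91.0% |
| 50% | about 121 | 13.9% | 244 | 91.9% |
| 75% | about 130 | 7.0% | 252 | 92.7% |

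**4. Precision at half recovery.**
- Stress case, 6-month values alone: √(101/120.5) = 0.916, so the standard error falls by about 8%.
- Stress case, the plan's ESS basis: √(227/244) = 0.965, a fall of about 3.5%.
- Milder case with 13.8% missing, 6-month values alone: √(120.7/130.3) = 0.962, a fall of about 4%.

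**5. Who could be recovered by look-back.** The permanent drop-out pattern that reproduces 227 contains nobody who misses month 6 and attends month 12. In that scenario every recovered value comes from remote contact.

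**The case against.** The D.8 sentence describes the intended mode; it does not prohibit anything. A reader might infer that a telephone interview is barred or that the value is irretrievably lost. The documents do not say so; they are silent. The loss follows from applying the plan as written, with no instruction to do otherwise.

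A reader might also infer that stopping CBT ends follow-up, or that Hypothesis 1a predicts unequal follow-up between arms. Neither is supported. Section F tests Hypothesis 1a on counselling sessions completed. No section ends follow-up when sessions stop, D.8.7 still collects an alliance measure from people who leave treatment early, and follow-up visits are paid for separately. A link between arm and missing follow-up is plausible but inferred.

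The 28% comes from a scenario that Section F itself regards as worse than expected, and the team's own retention record points to about 14%. The 8% gain in precision applies only to 6-month values taken alone in that stress case. These objections stand and limit the size of the point.

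In-person visits also have a purpose: a remote report of low-risk drinking would enter the primary outcome without PEth at that visit, and such cases could cluster in one arm. That is a real cost, but a self-report flagged by mode carries more information than no report. D.8.8 uses PEth to check claims of low-risk drinking, so a telephone report of heavy drinking loses little by its absence.

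Finally, Section F anticipates missing follow-ups and plans likelihood methods, imputation and sensitivity analyses. These show how far results depend on the missing-data approach; they cannot replace the observations.

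**Conclusion.** The point holds as a gap that is cheap to close. The plan names one mode and no fallback for an interview-based primary endpoint that can be taken remotely. The 6-month value would be missing for 28% of participants in the plan's stress case, and for about 14% to 21% under the D.10 loss rates with constant loss per visit.

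If half the missed interviews were recovered, those shares would halve. The recovery rate has no basis in the documents, so the range in the table matters more than any single row. The gain in power is minor, and the argument rests on reducing bias from absence that is plausibly tied to drinking. Its direction and size cannot be derived from the documents.

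Recovering a missed window at the next attended visit should not be counted on. It helps only those who return, and the month-12 interview would have to reach back 6 to 7 months. D.8.8 does not state the Timeline Follow-back window.

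**What to change.** Amend D.8 along these lines: follow-ups take place in person where possible; if a participant does not attend within the visit window, study staff complete the 30-day Timeline Follow-back and the EuroQol by telephone or video; this applies whether or not the participant has stopped CBT or mCM.

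Record the mode of each interview. Add to Section F a sensitivity analysis of the primary contrast restricted to in-person interviews, and report mode by arm. Look-back at a later visit can be kept as a secondary option, with the recall length recorded.

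PEth collection and the conditions of the long-term incentive payment stay as they are.

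The cost is protocol and IRB wording, one recorded variable, and short calls by existing staff. The downside is that remote cases have no PEth result at that visit, so a remote report of low-risk drinking is unverified; the mode record and the sensitivity analysis make that visible.
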